6.1.1 Treatment Groups

Data collected up to Week 16 visit will be analyzed by treatment groups based on the subject’s treatment in Part I of the study:

- Placebo
- SCD-044 █ mg
- SCD-044 █ mg
- SCD-044 █ mg

Data collected after Week 16 visit (i.e., Parts II) will be analyzed by treatment groups based on the subject’s treatment in Part I and the subject’s treatment in Part II of the study:

- Placebo/SCD-044 █ mg
- Placebo/SCD-044 █ mg
- SCD-044 █ mg
- SCD-044 █ mg
- SCD-044 █ mg

Adverse events and concomitant medications will be additionally analyzed for the entire study. Details are provided in the sections 6.12.1 and 6.12.6.

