12. The use of concomitant medications since the previous study visit will be documented and assessed. (See Section 4.5 and 5.8)
13. The Subject's body weight will be measured while the Subject is lightly clothed (e.g., no coat or shoes)

14. A urinalysis dipstick will be performed and evaluated at a site (See Section 5.5)
15. A [REDACTED] sample will be collected for [REDACTED] (See Section 3.1 and 5.5)
16. A [REDACTED] sample will be collected for [REDACTED] (See Section 6.3)
17. A blood sample will be collected within one hour before dosing for [REDACTED] (See Section 5.14)

19. Study drug administration in a clinic before 12 noon (See Section 8.5)

20. The following will be dispensed during [REDACTED]

- The study drug assembled for Visits 10, 11, 12, and 13
- A diary card with instructions and to record the study drug use, health changes and concomitant medication

21. A general safety review before discharge

7.1.7 [REDACTED] Visit [REDACTED]

1. The occurrence of all AEs & AESIs will be assessed and documented following the procedures in Sections 5.9, 10.1, and 10.3.
2. A query for PML (progressive multifocal leukoencephalopathy) will be performed (See Section 5.10)
3. A query for PRES (Posterior reversible encephalopathy syndrome) will be performed (See Section 5.11)
4. The Subject's diary provided at the previous visit will be collected and reviewed.
5. The returned study drugs will be counted
6. The use of concomitant medications since the previous study visit will be documented and assessed. (See Section 4.5 and 5.8)
7. Vital signs (blood pressure, pulse, respiratory rate and oral body temperature) will be documented. Subjects must remain in a seated or supine position for at least 5 minutes before vital signs are obtained. (See Section 5.3)

8. A blood sample will be collected for Hematology (See Section 3.1 and 5.5)

[REDACTED]

[REDACTED]

[REDACTED]

[REDACTED]

10. The following will be dispensed during [REDACTED]

- The study drug assembled for [REDACTED]
- A diary card with instructions and to record the study drug use, health changes and concomitant medication

11. A general safety review before discharge

[REDACTED]

[REDACTED]

7.1.8 [REDACTED] Visit [REDACTED]

The following procedures will be performed at [REDACTED]

1. A urine pregnancy test will be conducted for all females of childbearing potential (see Section 5.5)
2. Subject Reported Assessments will be collected for:
[REDACTED]

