6.9.2.4 Time to EASI75, EASI90, vIGA, and PP-NRS responses

Time to achieve EASI75 and EASI90, and time to achieve vIGA and PP-NRS responses will be summarized separately for the Part I of the study, for the Part II for subjects re-randomized at Week 16 and for the study overall for subjects assigned to SCD-044 at the Baseline.

In the analysis of Part I subjects will be analyzed by treatment groups based on the treatment that the subject received in Part I (see [Section 6.1.1](#)). Time to achieve EASI75 will be defined as the number of weeks from the day of the first dose of the study drug to the first EASI assessment in Part I (i.e., up to and including Week 16 visit) when EASI75 is achieved. For subjects who never achieve EASI75 in Part I the time will be censored at the last EASI assessment in Part I. Similar algorithm is used to define time to achieve EASI90.

Similarly, time to achieve vIGA response in Part I will be defined as the number of weeks from the day of the first dose of the study drug to the first vIGA assessment in Part I (i.e., up to and including Week 16 visit) when vIGA score of ‘clear’ or ‘almost clear’ with at least two-grade reduction from Baseline is achieved. For subjects who never achieve vIGA response in Part I the time will be censored at the last vIGA assessment in Part I.

Similarly, time to achieve PP-NRS response in the severity of itching in Part I will be defined as the number of weeks from the day of the first dose of the study drug to the first PP-NRS assessment in Part I (i.e., up to and including Week 16 visit) when severity of itching recorded in PP-NRS with at least four-point (or at least three-point) reduction from Baseline is achieved. For subjects who never achieve PP-NRS response in Part I the time will be censored at the last PP-NRS assessment in Part I.

The analysis for Part II will be conducted only for subjects who were initially randomized to placebo and switched to active treatment in Part II. In this analysis subjects will be analyzed by treatment groups based on their treatments in Part II (see [Section 6.1.1](#)). Times will be defined similarly to the analysis of Part I, except they will start at the time of the switch to a new treatment in Part II and will be censored at the last assessment in the study. Part II baseline will be used when determining EASI and vIGA responses.

[figure not shown]

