6.12.1 Adverse Events

Adverse events will be coded using MedDRA, Version 25.0, AE coding system for purposes of summarization.

An AE will be considered as treatment-emergent (TEAE) if the date of onset is on or after the date of the first study drug administration. AEs with unknown start dates will be counted as treatment-emergent unless the AE resolution date is prior to the study drug start date. If the start date is partially missing, the AE will be considered treatment-emergent, unless the month and year (when available) rule out the possibility that the event occurred post start of study drug dosing.

A TEAE is defined as treatment-related if its relationship to study medication is recorded as “Possible”, “Probable” or “Definite” on the eCRF. In case the relatedness was not assessed, the most conservative result (related) will be chosen for the analysis.

Cardiovascular AEs will be defined as AEs with MedDRA system organ class “Cardiac disorders” or “Vascular disorders”.

Adverse events that are of special interest, that represent signs/symptoms of Progressive Multifocal Leukoencephalopathy (PML) or of Posterior Reversible Encephalopathy Syndrome (PRES) and that are cardiac arrhythmias will be marked on the eCRF.

Events will be assigned to Part I or Part II of the study based on the date of onset, i.e. AEs that start prior to the first dose of the Part II treatment will be assigned to Part I and AEs that start on or after the date of the first Part II dose will be assigned to Part II.

In summaries of TEAEs a subject experiencing the same AE multiple times on the same treatment will only be counted once for that preferred term and treatment. Similarly, if a subject experiences multiple AEs within the same system organ class on the same treatment that subject will be counted only once in that system organ class and treatment. When summarizing AEs by severity, only the most severe occurrence within the preferred term or system organ class and treatment will be used. Similarly, when summarizing AEs by relationship to study drug, only the most related occurrence within the preferred term or system organ class and treatment will be selected for displays in summary tables.

All AE summaries will be presented in 3 ways:

1. For events in Part I only, using Part I treatment groups, with the additional groups SCD-044 Any Dose (including the three SCD-044 groups) and Total (including all subjects).

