6.12.2 Laboratory tests

A central laboratory will be used for all assessments unless noted otherwise. Unscheduled laboratory assessments can be performed at discretion of the Investigator in response to AEs. The laboratory assessments include:

Hematology: at all on-site study visits a blood sample will be collected for total and differential WBC count, Absolute Neutrophil count (ANC), ALC, Platelet count, Hemoglobin, Hematocrit, Mean Corpuscular Volume (MCV) testing. Additionally, total WBC count with differential counts including ALC and ANC counts will be performed pre-dose and at 1h, 2h, 4h and 6h post-dose on Day 29 (Week 4).

Lipid profile: at the study visits 1, 2, 10 and 17 (Screening and study weeks 0, 16, and 32) a blood sample will be collected for LDL, HDL and total cholesterol and Triglycerides testing.

Clinical chemistry: at the study visits 1, 2, 7, 8, 10, 15, 16, and 17 (Screening and study weeks 0, 4, 8, 16, 20, 28, and 32) a blood sample will be collected for sodium, potassium, chloride, calcium, magnesium, bicarbonate, phosphate, blood urea nitrogen, random glucose, albumin, total protein, alkaline phosphatase, creatinine, ALT, AST, gamma glutamyl transferase (GGT), total bilirubin, conjugated bilirubin testing.

Coagulation profile: at the study visits 1, 2, 10, and 17 (Screening and study weeks 0, 4, 16, and 32) a blood sample will be collected for PT, INR, and aPTT testing.

Serology: at Screening visit a blood sample will be collected for: anti-VZV IgG, HIV antibodies, HBsAg, and HCV antibodies testing.

QuantiFERON Gold test: at Screening Visit a blood sample will be collected for TB antigens testing. A maximum of 2 QuantiFERON tests are allowed. A retest is permitted if the first is indeterminate; the result of the second test will be used. Chest X-ray should be performed for subjects with a positive or 2 successive indeterminate QuantiFERON test results; a chest X-ray is acceptable if performed within the past 3 months and available at a site along with an associated report.

Serum pregnancy test: at Screening Visit a blood sample will be collected for serum beta-hCG testing.

The following tests will be performed at a clinic site:

Urinalysis dipstick: at the study visits 1, 2, 10, and 17 (Screening and study weeks 0, 16, and 32) a urine sample will be collected for pH, specific gravity, protein, glucose, ketones, and blood testing.

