6.12.8 Ophthalmological Examination

[figure not shown]
At the study Visits 1, 9 and 17 (Screening and study Weeks 12 and 32) a complete ophthalmologic examination will be performed by an ophthalmologist, including an ophthalmological history, best corrected visual acuity (Snellen chart), ophthalmoscopy (preferably slit-lamp) and Optical Coherence Tomography (OCT) assessment (measurement of central foveal thickness).

The following results of the ophthalmological examination will be summarized descriptively by eye (left or right), visit and treatment group:

- Best corrected visual acuity (Snellen denominator)
- OCT results: central fovea thickness

Number and percentage of subjects with presence of macular edema and/or uveitis will be presented by visit and overall across all visits (including both scheduled and unscheduled visits).

All ophthalmological examination data will be listed.

Number and percentage of subjects requiring monitoring beyond 6 hours will be provided along with reasons, treatment group and visit as well as overall across all visits.

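### SAP 6.1.1 separates Part I from Part II by visit, but placebo switchers appear to take their first Part II dose during the Week 16 visit, so post-dose monitoring data from that day default to Placebo

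*SAP*

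**What the plan says.** SAP 6.1.1 gives two rules. The first is "Data collected up to Week 16 visit will be analyzed by treatment groups" defined by the Part I assignment, with a Placebo column. The second is "Data collected after Week 16 visit (i.e., Parts II) will be analyzed by treatment groups" defined by both assignments. Under it the placebo subjects appear only as two Placebo/SCD-044 groups. Neither rule mentions a dose or separates pre-dose from post-dose data within the Week 16 visit.

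Other parts of the SAP place the boundary at the dose:
- Adverse events (6.12.1): "AEs that start on or after the date of the first Part II dose will be assigned to Part II".
- Concomitant medications (6.12.6) are divided at the first Part II dose.
- The Part II baseline (6.1) is the last assessment before the first Part II dose, and is used for Part II findings in placebo switchers.
- Part II time-to-response (6.9.2.4) is counted from the switch.

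The closing text of the safety section, after the ophthalmology paragraphs, says: "Number and percentage of subjects requiring monitoring beyond 6 hours will be provided along with reasons, treatment group and visit", and adds a summary over all visits. It states no Part I/Part II split. The contents list has a dose-monitoring section, 6.12.9, at this place.

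**The concern.** If the first SCD-044 dose of a placebo switcher is taken during the Week 16 visit, what is observed in the following hours is a response to SCD-044. A visit-based cut files it under Placebo, the reference column, and removes it from the Placebo/SCD-044 group it describes. The same occurrence could then be a Placebo/SCD-044 adverse event in one table and a Placebo monitoring finding in another.

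This matters because first-dose observation is a central safety display for this drug class. The SAP excludes subjects with a heart rate below 55 bpm because of class effects, and it lists a separate visit schedule for subjects at higher risk of bradyarrhythmia. Under SAP section 7 the Part I tables are produced once the last subject completes Week 16, so a misplaced result would enter the first unblinded report.

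**Working it through.** The plan gives no figure to reproduce. The check is a tracing of rules.

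**1. Does the first rule in 6.1.1 include the Week 16 visit?** It does not say so outright, but it must. The primary endpoint is a Week 16 comparison with placebo, and a Placebo column exists only under the first rule. SAP 6.2 equates completing Part I with attending Week 16. SAP 6.9.2.4, for time to response, spells it out: "first EASI assessment in Part I (i.e., up to and including Week 16 visit) when EASI75 is achieved".

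**2. Is the visit in Protocol 7.1.6 the Week 16 visit?** Its number is redacted, but the evidence agrees.
- Protocol 7.1.5 dispenses drug for Visit 9, and 7.1.6 dispenses drug for Visits 10 to 13.
- SAP 6.12.2 schedules the lipid profile "at the study visits 1, 2, 10 and 17 (Screening and study weeks 0, 16, and 32", so Visit 10 is Week 16. It schedules the urine dipstick at the same visits, and 7.1.6 item 14 is a dipstick.

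**3. Is a dose given at that visit?** Item 19 of 7.1.6 reads "Study drug administration in a clinic before 12 noon (See Section 8.5".

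**4. Is it the first Part II dose?** This is inferred. SAP 6.12.1 starts the three weekly sections of the Part II start-up table at the Week 16 visit and says that only the two Placebo/SCD-044 groups go through that period.

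**5. Which rule governs each type of data at Week 16 for a placebo switcher?**

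| Data | Boundary in visible text | Column for post-dose Week 16 data |
|---|---|---|
| Adverse events (6.12.1) | first Part II dose date | Placebo/SCD-044 |
| Concomitant medications (6.12.6) | first Part II dose date | Part II |
| Monitoring beyond 6 hours | none of its own, so 6.1.1 | Placebo, read literally |
| Vital signs, ECG | section not visible | unknown; 6.1.1 if no specific rule |

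**6. How many subjects?** About 240 subjects are planned (Protocol 4.1), allocated 3:1:1:3 to placebo, low, intermediate and high (SAP 3.1). Placebo: 240 × 3/8 = 90. That is an upper limit, since only those who reach Week 16 and are re-randomised are affected, and no dropout rate is visible.

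**7. Which rows are exposed?** The monitoring summary is by visit, so rows before Week 16, including the first dose at Baseline, are correct under any reading. The Week 16 row and the all-visits row are exposed.

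**The case against.** The best defence is that the SAP read as a whole puts post-dose Week 16 data in Part II. Section 6.1.1 itself glosses its second category as Part II, 6.1 provides a Part II baseline for switchers, 6.12.1 counts Week 16 in the Part II start-up period, and 5.1 analyses safety by treatment actually received. A programmer might well do the right thing. But 5.1 does not say when a subject changes column, and 6.1.1, the only general rule, contradicts the dose-based sections. The intention is probably right; the stated rule does not carry it out.

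The second defence is that much is not visible: the vital-sign and ECG sections, the opening of the dose-monitoring section, the visit schedules and the table shells. Protocol 7.1.6 shows no numbered post-dose measurement between dosing and discharge. It also does not label its in-clinic dose as the first of Part II, and the end-of-treatment visit (7.1.10) includes an in-clinic dose too. This stands. It limits the point to a rule that needs to be reconciled, and a specific rule may already exist.

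A reader might infer that all Week 16 data of switchers are reported as placebo data. The documents do not support that: adverse events, including arrhythmias and events of special interest recorded as such, and concomitant medications are split at the dose.

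**Conclusion.** The point holds as an internal inconsistency with a limited reach. Followed literally, 6.1.1 reports post-dose Week 16 monitoring of placebo switchers under Placebo, while the rest of the SAP splits at the first Part II dose. In the visible text the exposure is two rows of one table and at most about 90 subjects. Primary and key secondary efficacy are not in question, because Week 16 efficacy belongs in Part I under either rule.

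The conclusion assumes that the dose in Protocol 7.1.6 is the first Part II dose, that monitoring follows it, and that no unseen section overrides 6.1.1. A reader might go further and infer that the active-placebo contrast in extended monitoring would shrink or reverse. That needs event rates by arm, retention to Week 16 and the layout of the all-visits row, none of which the documents give. Only the direction of the error can be stated: responses to SCD-044 would enter the placebo column.

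**What to change.** In SAP 6.1.1, define the Part I/Part II boundary by the date and time of the first Part II dose. Week 16 data collected before that dose go to the Part I arm. Week 16 safety data collected after it go to the Part I/Part II group, using the Part II baseline for switchers. Date alone is not enough for visit-based data, because pre-dose and post-dose assessments share the date; a dose time or a pre-/post-dose flag is needed.

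State that the rule covers the dose-monitoring summary and any post-dose vital signs and ECG, and show the all-visits row of the monitoring summary separately for Part I and Part II. If an unseen section already does this, make 6.1.1 agree with it.

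The cost is a few lines of SAP text and one derivation rule. No new data should be needed, provided that dose times or pre-/post-dose flags are recorded.

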6.1.2 Adjustment for multiplicity

No adjustment for multiplicity will be needed for the analysis of the primary and key secondary endpoints due to the step-down testing approach described in [Section 6.9.1.1](#). P-values for other endpoints, if calculated, will be presented nominally, without multiplicity adjustment. No inferences will be drawn from these p-values.

6.1.3 Handling of Withdrawals and Missed Data

In the primary analysis of the primary and the key secondary endpoint subjects with missing endpoint will be treated as non-responders. For more details see section 6.9.1.1. Last Observation Carried Forward (LOCF) and Active Treatment Worst Case (ATWC)

imputations will be explored in the sensitivity analyses (see section 6.9.1.2). All other endpoints will be summarized as collected without imputations.

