6. STATISTICAL METHODS OF ANALYSIS

6.1 General Principles

The statistical analyses will be performed by [REDACTED] with approval of the Sponsor, using SAS® Version 9.4 (or higher). All tables, figures and listings will be produced in landscape format.

In general, all data will be listed by subject and visit/time point where appropriate. The summary tables will be stratified by, or have columns corresponding to, treatment groups.

The total number of subjects in the treatment group (N) under the specified population will be displayed in the header of summary tables.

Data will be summarized using descriptive statistics for continuous variables. Unless otherwise specified, descriptive statistics will include number of subjects, mean, standard deviation, minimum, median, and maximum. Number of subjects with missing values will also be displayed, but only if non-zero. The minimum and maximum statistics will be presented to the same number of decimal places as the original data. The mean and median will be presented to one more decimal place than the original data. The standard deviation will be presented to two more decimal places than the original data.

In summary tables of categorical variables, counts and percentages will be displayed. The count [n] indicates the actual number of subjects in a particular category, which should always be less than or equal to the total number of subjects in the respective study group with known (non-missing) category [M]. Percentage will be obtained by: % = $n/M*100$. Unless otherwise specified, all percentages will be expressed to one decimal place.

All statistical tests will be two-sided at a significance level of $\alpha = 0.05$, unless otherwise indicated.

Baseline will be defined as the last assessment, scheduled or not, prior to the first dose of the study drug, unless otherwise specified. This notion of baseline will also be referred to as Part I baseline. Part II baseline will be defined as the last assessment, scheduled or not, prior to the first dose of the study drug in Part II. Part II baseline will be used in analysis of findings collected in Part II for subjects initially randomized to Placebo and re-randomized to SCD-044

(█ mg or █ mg) in Part II. Throughout this SAP, if the word “baseline” is used without qualification “Part I” or “Part II”, it will refer to Part I baseline.

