6.9 Efficacy Analyses

6.9.1 Analysis of the primary and key secondary endpoints

6.9.1.1 Primary analysis

The primary analysis will be performed on the ITT population.

Subjects in the ITT population with missing EASI at Week 16 or missing baseline will be imputed as non-responders for the primary endpoint. Similarly, subjects in the ITT population with missing vIGA at Week 16 or missing baseline will be imputed as non-responders for the key secondary endpoint.

Additionally, the subjects with intercurrent events, i.e. those who took any rescue medications (systemic or topical) prior to Week 16, took any prohibited medications prior to Week 16 (as determined by blinded data review) and discontinued the study drug prior to Week 16 will be considered non-responders for both the primary and key secondary endpoint. Subjects will be known to take systemic rescue medications prior to Week 16 if this is recorded at the “Rescue Medications” CRF or “Concomitant Medications” CRF or the subject attended any of “Systemic Rescue Medications Visits” 7 to 10. Topical rescue medications will be identified through a review of the “Concomitant Medications” CRF.

For both primary and key secondary endpoint the number and percentage of subjects achieving the endpoint will be provided. Comparisons between each active group and the placebo group will be performed pairwise. Each comparison will be done using Cochran-Mantel-Haenszel (CMH) test stratified [REDACTED]

If all strata have no subject in one of the treatment groups, a value of 0.1 will be added to all cells in the corresponding table in order to prevent dividing by 0, as suggested in Greenland and Robins (1985). The estimates of Mantel-Haenszel common risk (response rate) difference between each active dose group and placebo, along with 95% confidence interval, will be provided. The p-value from the Breslow-Day test for homogeneity of strata will also be provided. If the p-value of the Breslow-Day test is ≥ 0.05 , the treatment-by-strata interaction is not significant. In the case of heterogeneity between the strata, in-depth analysis will be conducted to understand the source of the interaction; Fisher’s exact test will be used instead of CMH.

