6.9.1.2 Sensitivity analyses

The following sensitivity analyses will be performed to explore the effects of missing data on the primary endpoint and the key secondary endpoint:

1. Analysis similar to the primary analysis on the ITT population, but with missing endpoints imputed using Last Observation Carried Forward (LOCF) approach. For this

analysis the latest available post-baseline assessment of EASI will be carried forward to impute missing Week 16 assessments. Subjects with missing baseline or no post-baseline assessment prior to Week 16 will be excluded from this analysis. Additionally for subjects with intercurrent events, i.e. those who took topical or systemic rescue medications prior to Week 16, took prohibited medications prior to Week 16 or discontinued treatment prior to Week 16 the last available post-baseline assessment obtained prior to the start of the rescue medication will be used to impute Week 16 assessment. If no post-baseline assessment obtained prior to the intercurrent event (start of rescue medication, start of prohibited medication, discontinuation of treatment) is available, such subject will be excluded from this analysis.

2. Analysis similar to the primary analysis on the ITT population, but with missing endpoints imputed using Active Treatment Worst Case (ATWC) approach. For this analysis any subjects in the Placebo group with missing response or with an intercurrent event will be imputed as responders, while any subjects in any active treatment group with missing response or with an intercurrent event will be imputed as non-responders.
3. Tipping point analysis. This analysis will consist of a series of analyses similar to the primary analysis of the primary and key secondary endpoints with varying proportions of subjects with missing endpoint value or with intercurrent events imputed as responders or non-responders. The analysis will be performed for each active treatment group vs. placebo and for each combination of X1, the percentage of subjects with missing endpoint value or with intercurrent events in the placebo group and X2, the percentage of subjects with missing endpoint value or with intercurrent events in the active group. Both X1 and X2 will range from 0% to 100% in steps of 25%.

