6.9.2.5 Relationship between SCD-044 plasma concentrations and efficacy/PD endpoints

subjects with intercurrent events prior to the analysis timepoint will be excluded from the analysis.

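### The other Week 16 responder endpoints are summarised as collected, with no visible intercurrent-event rule and no planned difference from placebo

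*SAP*

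**What the plan says.** For the primary and key secondary endpoints, SAP 6.9.1.1 counts a missing baseline or Week 16 value as non-response. Subjects who took rescue or prohibited medication, or stopped study drug, before Week 16 "will be considered non-responders for both the primary and key secondary endpoint". Estimands are defined only for these two endpoints (2.2 and 2.4). For the rest, 6.1.3 states: "All other endpoints will be summarized as collected without imputations".

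The other binary endpoints are listed in 6.9.2.2 and use the ITT population (6.9.2). The list also contains EASI-75 and vIGA response, with no restriction on visit. The planned output is a count, a percentage and a binomial 95% CI for each arm. Under 6.1, percentages are n/M, where M counts only subjects with a non-missing value. The same section adds: "The total number of subjects in the treatment group (N) under the specified population will be displayed in the header of summary tables".

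Differences from placebo are planned for the other endpoint types. For the primary and key secondary endpoints, 6.9.1.1 provides "The estimates of Mantel-Haenszel common risk (response rate) difference between each active dose group and placebo", with a 95% CI. For continuous endpoints, 6.9.2.1 provides MMRM differences at Week 16. On p-values outside the hierarchy, 6.1.2 says: "No inferences will be drawn from these p-values".

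Two other analyses state an event rule of their own. In the LOCF analysis (6.9.1.2), for subjects with events, "the last available post-baseline assessment obtained prior to the start of the rescue medication will be used to impute Week 16 assessment". In the concentration-response section (6.9.2.5), "subjects with intercurrent events prior to the analysis timepoint will be excluded from the analysis".

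**The concern.** One report would show Week 16 responder rates on two bases. EASI-75 and vIGA response would be composite rates over all randomised subjects. EASI-90, PP-NRS response and the others would be observed-case rates in which, on the natural reading, a response reached after rescue or prohibited medication counts as success. EASI-75 and vIGA response could themselves appear at Week 16 under both rules, with nothing to say which rate is the reported one.

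This is a dose-ranging study, and the supporting responder endpoints are read against placebo. Separate per-arm intervals do not supply that comparison. What is at stake is how clearly the supportive evidence can be interpreted, not the confirmatory result.

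**Working it through.** The plan states no figure to reproduce. Every event and response rate below is an assumption.

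**Arm sizes.** About 240 subjects (protocol 4.1) at 3:1:1:3 (SAP 3.1): 240 × 3/8 = 90 for placebo and for high dose; 240 × 1/8 = 30 for low and for intermediate dose.

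**Missing values.** Suppose 18 of 90 subjects have no Week 16 value and 14 of the rest respond. The n/M rule gives 14/72 = 19.4%. Missing-as-failure gives 14/90 = 15.6%. Since n and N are both displayed, a reader can recover the second figure.

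**Post-event values.** Assume no missing data, so that only the event rule differs. Let r be the share of post-event values that are responses, equal in both arms. Then:

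- as-collected rate = (responders under 6.9.1.1 + r × events)/90
- shift in the difference = r × (active events − placebo events)/90

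Take EASI-90 under 6.9.1.1 as 5/90 = 5.6% on placebo and 15/90 = 16.7% on high dose, a difference of 11.1 points.

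| Events, placebo / high | r | Placebo | High dose | Difference | Shift |
|---|---|---|---|---|---|
| any | 0 | 5/90 = 5.6% | 15/90 = 16.7% | 11.1 | 0 |
| 9 / 9 | 1/3 | 8/90 = 8.9% | 18/90 = 20.0% | 11.1 | 0 |
| 18 / 9 | 1/9 | 7/90 = 7.8% | 16/90 = 17.8% | 10.0 | −1.1 |
| 18 / 9 | 1/3 | 11/90 = 12.2% | 18/90 = 20.0% | 7.8 | −3.3 |
| 9 / 18 | 1/9 | 6/90 = 6.7% | 17/90 = 18.9% | 12.2 | +1.1 |
| 9 / 18 | 1/3 | 8/90 = 8.9% | 21/90 = 23.3% | 14.4 | +3.3 |

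The value r = 1/3 is extreme for EASI-90: with 18 placebo events, the event-free placebo rate is 5/72 = 6.9%. For a commoner endpoint r could be higher. With event-free response of 25% and 45%, events in 20% and 10%, and r = 1/2, the composite rates are 0.80 × 25% = 20.0% and 0.90 × 45% = 40.5% (20.5 points). The as-collected rates are 20.0 + 10.0 = 30.0% and 40.5 + 5.0 = 45.5% (15.5 points).

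**Nested endpoints.** Let placebo EASI-75 under 6.9.1.1 be 10/90 = 11.1%. EASI-90 as collected exceeds it once at least 6 post-event EASI-90 responses are added: (5 + 6)/90 = 12.2%. Those 6 subjects are also EASI-75 responders, so EASI-75 as collected would be at least (10 + 6)/90 = 17.8%. The reversal therefore appears only when the 6.9.2.2 EASI-90 rate is set beside the 6.9.1.1 EASI-75 rate. Within 6.9.2.2 it cannot occur.

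**Per-arm intervals against a difference.** At assumed rates of 20% and 35% with 90 per arm, the per-arm Wald 95% CIs are 11.7–28.3% and 25.1–44.9%, which overlap. The difference is 15 points with SE = √(0.20 × 0.80/90 + 0.35 × 0.65/90) = 0.0656, so its CI is 2.1 to 27.9, which excludes 0. In a 30-subject arm, 3/30 against 5/90 is 4.4 points with SE = √(0.10 × 0.90/30 + 0.0556 × 0.9444/90) = 0.0599 and CI −7.3 to 16.2.

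**The case against.** The sentence in 6.1.3 sits under withdrawals and missing data and speaks of imputation. It does not say that post-event responses count. That is right: the reading is an inference, drawn from that sentence together with an event rule confined to two endpoints. It has some support. LOCF needs a separate event rule only if post-event values can exist, and 6.9.1.1 refers to systemic rescue visits 7 to 10, numbers that in the main schedule reach Week 16. Neither proves that such values will be recorded.

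A reader might infer that responses after stopping study drug count too. The visible text does not support that. Subjects who leave the study go to an Early Discontinuation visit and then Follow-up (SAP 3.1), and by-visit summaries use scheduled visits only (6.1). Such values matter only if those subjects are still assessed at Week 16, which is not shown.

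A reader might also infer that the plan makes EASI-90 and EASI-75 incoherent. It does so only across the two tables, as worked above.

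The size is assumed and its direction is not determined. The unstratified 95% half-width for 5/90 against 15/90 is 1.96 × √(0.0556 × 0.9444/90 + 0.1667 × 0.8333/90) = 9.0 points, so even a 3.3-point shift lies well inside it. The missing contrast is partly a matter of preference, since EASI, SCORAD and DLQI already have MMRM differences. The fix also leaves percent change in EASI as collected. These points stand and lower the priority.

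Most endpoint weeks in SAP 4.3 are redacted, although Week 16 is visible for DLQI 0/1. Redacted text could hold a further rule.

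**Conclusion.** The concern holds in limited form. For the non-key binary endpoints, the visible plan gives no intercurrent-event rule and no difference from placebo. Missing subjects drop out of the denominator, and responses after rescue or prohibited medication would, by inference, count. The missing-data part and an unstratified difference can be rebuilt from n and N. The event handling and the stratified difference cannot be rebuilt from those tables.

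In the EASI-90 examples the difference is unchanged when post-event responses are equal. With events differing by 9 subjects, it shifts by about 1 point at r = 1/9 and by about 3 points only at the extreme r = 1/3, in either direction. The commoner-endpoint example gives 5 points, with half of post-event values assumed to be responses. These endpoints are descriptive, so nothing here touches the confirmatory tests or type I error. Priority is low to moderate.

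**What to change.** Amend SAP 6.9.2.2 for the Part I non-key binary endpoints at Week 16:

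- Make the 6.9.1.1 rule the main summary: missing value or intercurrent event is non-response, with all ITT subjects in the denominator.
- Keep observed cases as a supportive summary, labelled to say whether post-event values are included.
- Add the stratified Mantel-Haenszel risk difference for each dose against placebo with a nominal 95% CI. Where counts are sparse (for example, fewer than 5 responders in the two arms combined), give an unstratified difference with a Newcombe interval.
- State that the 6.9.1.1 rates are the reported Week 16 EASI-75 and vIGA results wherever 6.9.2.2 repeats them.

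The cost is SAP wording and modest programming that reuses the existing event flags and Mantel-Haenszel code for about ten responder definitions and three doses. Reported rates will be slightly lower, missing values count as failure (hence the supportive summary), and intervals will be wide in the arms of about 30 subjects.
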